Drs. [name], [name] and [name] will work closely with the statistician ([name]) to design forms and a database that maximize accurate data entry. Common data elements will use the standardized codes and attempts will be made to harmonize all database codes with NIH initiatives. To minimize data-entry error and data-management miscoding, questionnaire data will be collected via tablet computers and immediately uploaded to a secure web-based server, ensuring backup. The electronic files from all sites will be merged into one REDCap data management file. Summary results will be entered into the larger REDCap database. Source documents and electronic data will be checked for accuracy and adherence to study protocols.

Data Storage:

Consent forms and subject lists will be stored in locked file cabinets separate from subject data and on password-protected computers, and will be only accessible to the research team. All subject data will be labeled only with a code number. These coded data will be kept separate from the master list that links subjects and their code numbers. All subject data will be kept in locked file cabinets in a locked office. Coded data stored on the computer will be maintained in password-restricted files. Any breach in confidentiality will be reported to the PIs.

Statistical Considerations

The primary outcome will be systolic BP at 12 months and secondary outcome will be non-HDL cholesterol at 12 months, both measured at 4 time-points (0, 4, 8, and 12 months). All BPs used for outcomes will be obtained by a blinded research assistant and cholesterol levels will be measured by lab personnel who are also blinded to treatment group. Because the outcomes are continuous, linear mixed-effects models⁸⁹ (LMM) will be used to examine the differences over time between the study arms. LMM will allow us to implicitly account for the correlation between a patient's repeated measurements over time. The general mean structure of the LMM we will use to examine the hypotheses is, $Y_{ij} = \beta_0 + \beta_1 * I(month = 4) + \beta_2 * I(month = 8) + \beta_3 * I(month = 12) + \beta_5 * arm * I(month = 4) + \beta_6 * arm * I(month = 8) + \beta_7 * arm * I(month12)$, where Y_{ij} represents the outcome of interest (i.e., SBP or non-HDL) for patient i at time j. In this model, we fit a common intercept and arm is the intervention group indicator. Similarly, time is classified, where for example, $I(month = 12)$ is a dummy variable equal to 1 for the 12 month time point. Random intercepts will be included for

each individual to account for correlation among repeated measurements over time. The primary analytic model will adjust for clinic site. The mixed effects model parameters will be estimated and tested using SAS PROC MIXED (SAS Institute, Cary, NC), and the hypothesis of between-arm differences over time will be tested using estimate statements within PROC MIXED. In particular, β_7 , the estimated difference in outcome between arms at 12 months, will be the primary effectiveness outcome assessed.

For the tertiary outcome of cascade category, we will calculate an ordinal four-level variable at baseline, 4, 8, and 12 months. We will use a proportional odds model fit via generalized estimating equations to examine differences over time between study arms. The proportional odds assumption will be assessed using score tests, and the model will be relaxed to partial proportional odds if necessary. Robust sandwich standard errors will be used to account for potential overdispersion and correlation among the repeated observations over time. Similarly to the primary analysis, the model will adjust for clinic site and include the same general mean model specification. The primary hypothesis will be tested via SAS PROC GENMOD to assess whether the estimated proportions in each level at 12 months differ between arms. All analyses will be conducted following an intention to treat (ITT) principle.

Missing Data:

We will assess mechanisms for missing data in this study. LMM, implicitly accommodates missingness when the response is Missing At Random (MAR); that is, when missingness is due either to treatment, to prior outcome, or to other baseline covariates included in the LMM. We will address missing data by imputing missing values using multiple imputation procedures as described by Schafer. Once missing values have been imputed, each multiply-imputed data set can be analyzed using the LMM. Final parameter estimates and their standard errors will be calculated using Rubin's formula. We will analyze our data and report final study results with and without employing the multiple imputation strategy (compared to complete case analysis) and carefully examine and describe any discrepancies found.

Power:

The power calculation for this study was based on our prior nurse-led BP intervention¹², a meta-analysis of cholesterol medication adherence interventions⁴², and baseline blood pressure and cholesterol data from our clinic sites. Power estimates were derived empirically via simulation in SAS 9.4. Simulated data were generated based on estimates from prior studies, such that we assumed a mean SBP at baseline of 145mmHg for both arms, with a reduction in the education control arm of 1mmHg by 12 months. For the intervention arm, we evaluated effect sizes (differences from education control at 12 months) of 5-7mmHg. We estimate that 15% of patients may drop out by the 12-month time point, and incorporated missing values into the simulated data based on a uniform pattern of 5% missing at 4 months, 10% at 8 months, and 15% at 12 months. The drop-out rate is consistent with prior interventional studies at our sites (80-88% retention at 12 months).^{11,12,90} We conservatively estimated variance components assuming a total standard deviation of 17 and a within-individual correlation of 0.4 among repeated SBP measurements. Similarly, for the secondary non-HDL outcome, we assumed a baseline value of 132mg/dL with a standard deviation of 41 and a within-individual correlation of 0.7, and evaluated sample size needed over effect sizes ranging from 10-20mg/dL.

After generating 1,000 simulated datasets under these assumptions, we fit the LMMs described above to each and assessed the effect of interest using two-sided tests with a type I

error rate of 0.05. Based on results, we will have >80% power to detect a 6mmhg lower systolic BP and >90% power to detect a 15mg/dL lower non-HDL cholesterol in the intervention arm vs. education control. Table 5 displays the sample sizes needed to detect a range of plausible *clinically significant* BP and non-HDL effects. A 6 mmHg improvement in systolic BP is associated with a ~20% decrease in ASCVD events⁹¹, and a 15mg/dL improvement in cholesterol is associated with ~10% decrease in clinical ASCVD events³¹.

Table 5: Sample size estimates to detect a range of plausible and *clinically significant* effect sizes

	BP Effect Size			Non-HDL Effect Size		
	5mmHg	6mmHg	7mmHg	10mg/dL	15mg/dL	20mg/dL
70% Power	278	190	140	248	110	64
80% Power	350	234	178	310	148	80
90% Power	466	340	232	424	184	104

Green cells represent sample sizes that are less than our proposed sample size (n=300).

Pre-specified sub-group analyses of the primary, secondary, and tertiary outcomes will include clinic site, sex, and baseline ASCVD risk (<20% 10-year risk⁹² vs. >20% or prior ASCVD). For each category, we will examine the interactions with intervention arm and time. Generally, the modeling approach will mirror that described above for each outcome. Three separate analyses for each outcome will be conducted to assess the effect of each potential moderator. Models will be fit in SAS PROC MIXED and GENMOD, as described above, and the moderating effect of each of the three factors will be assessed via the hypothesis test of the three-way interaction among subgroup, treatment, and time at 12 months.

ClinicalTrials.gov requirements

This application includes a trial that requires registration in ClinicalTrials.gov. The registration number for this trial is NCT03643705.

Multiple Principal Investigator Leadership Plan

This project will have three NIH co-Principal Investigators (co-PI) and a fourth University Hospitals Principal Investigator to oversee the IRB:

1. **[name], MD (NIH contact PI)**—Associate Professor of Medicine; University of Washington School of Medicine; Seattle, WA
2. **[name], PhD (NIH MPI)**—Research Professor of Population Health, Medicine, Psychiatry, and Nursing; Department of Population Health Sciences; Duke University School of Medicine; Durham, NC
3. **[name], RN PhD (NIH MPI)**—Professor of Nursing; University of Washington School of Nursing; Seattle, WA
4. **[name], MD (UH IRB PI)**—Professor of Medicine; University Hospitals Cleveland Medical Center and Case Western Reserve University School of Medicine; Cleveland, OH

Rationale: We have chosen the multiple PI approach because developing innovative strategies to address the increasing burden of cardiovascular risk among people living with HIV (PLHIV) requires collaborative, interdisciplinary research. Furthermore, the two junior co-PI's ([name] and [name]) who are emerging as independent scientists in their field, will benefit from the experience of a senior implementation scientist ([name]) with a proven track record developing successful and scalable non-physician-led interventions to address cardiovascular risk factors in the VA and general US population.

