- **Healthcare team members (n=36).**

This mixed-methods aim will have two complimentary areas of focus:

- **Perceptions of ASCVD risk**
- **Barriers to and facilitators of high-quality ASCVD preventive care**

We will recruit up to **60 PLHIV** ($n=20$ from each site) to participate in a mixed-methods study. We will enroll until we achieve data saturation, where no new themes or explanations emerge. Based on previous work^{49,65-68}, this sample size more than sufficient to reach saturation. All PLHIV will have suppressed HIV viral load (<200 copies/ml), hypertension (SBP >130mmHg on two occasions in the EMR within the last year and/or on anti-hypertensive medication), AND hypercholesterolemia (non-HDL > NLA target (see **Table 1**) and/or on cholesterol medication). Additionally, up to **36 healthcare team members** (3 HIV MDs, 3 PCPS, 3 RNs and 3 support staff members from each site) will complete a key informant interview. PLHIV and care team members will be recruited by purposive and snowball sampling from the clinics in which they receive care and work. All subjects will be consented prior to enrollment.

Sub-Aim 1.1: Intervention adaptation

We will use a participatory, iterative design process⁶⁹⁻⁷¹ with a “design team” at Cleveland

(combined UH/Metro Design Team; ~12 members) and Duke (~6 members). Design team members may include research team members, HIV providers, primary care providers, nurses, PLHIV with hypertension and hypercholesterolemia, information technology experts, and any other key stakeholders TBD. The design process will involve three main phases: brainstorming, conceptualization, and creation described below in study procedures. Additional acceptability and feasibility testing will occur before and after a 6 week pilot intervention. These data will inform two additional design team meetings to iteratively refine the intervention.

Aim 2: Randomized controlled trial

HIV+ adult participants (n=300) on suppressive ART with both hypertension (confirmed systolic BP >130 mmHg and/or on treatment) & hypercholesterolemia (non-HDL cholesterol > National Lipid Association targets and/or on treatment) will be stratified by 3 clinic sites and randomized 1:1 to intervention vs. education control.

Aim 3: Descriptive Process Evaluation

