
The intervention will utilize many of the same procedures as for the parent EXTRA-CVD intervention (aim 2). Given that visits will be limited to remote means, however, the study team will not collect blood pressure or cholesterol outcome measurements. Study nurses will collect participant-reported, at-home BP measures and will provide CVD coaching and care coordination through telephone and/or videoconferencing during the 4-, 8-, and 12-month follow-up visits. For these follow-ups, the study team will send participants the REDCap survey links via e-mail or will administer surveys by telephone. Our team has experience doing this with the EXTRA-CVD study during the early COVID era (March-June 2020), when all study procedures were conducted remotely. These surveys include validated instruments assessing participants' experiences with loneliness, HIV self-management, and COVID-specific risks and lifestyle impacts. The only EXTRA-CVD surveys which will not be administered to aim 4 trial participants are the provider trust and communication surveys, which we believe cannot be

reliably and confidentially administered by telephone. CVD and HIV-related health information will be reviewed by the study nurses before each follow-up visit through the use of each site's electronic medical record (EMR). This study visit preparation using EMR review allows the study nurses to coordinate CVD care and medication management with the health team, and helps the nurse determine participant progress and elements where participants may benefit from CVD coaching during the virtual follow-up visits. Study nurses will coordinate CVD care with the participant's healthcare providers through email and/or EMR support tools, as is being done in aim 2.

Aim 4 Timeline

Invitations will be sent to the design team members in late October 2020, explaining aim 4 and capturing their interest in participating in the adaptation process. The study team expects to begin consenting design team members in November and to begin conducting study activities related to aim 4 adaptation in November and completing in December 2020.

The study team plans to begin recruitment and enrollment for the aim 4 intervention in January 2021 and continue recruitment for six months. In this scenario, the final 12-month follow-up study visits for aim 4 are expected to be completed in June 2022, and the process evaluation exit interviews to be completed by September 2022.

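### Aim 2 SBP and non-HDL models: with a random intercept alone, the 12-month standard error is guaranteed only under compound symmetry; an unstructured covariance is a cheap safeguard

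*Combined protocol and SAP*

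**What the plan says.** The point concerns Aim 2, in which 300 participants are "randomized 1:1 to intervention vs. education control". It does not concern the Aim 4 virtual arm, for which the "study team will not collect blood pressure or cholesterol outcome measurements".

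Under Statistical Considerations, SBP and non-HDL at 0, 4, 8 and 12 months are analysed with a linear mixed model in PROC MIXED. The mean model has a common intercept, categorical time and arm-by-time terms, adjusted for site. Its last coefficient, β7, is "the estimated difference in outcome between arms at 12 months, will be the primary effectiveness outcome assessed". The covariance is described in one sentence: "Random intercepts will be included for" "each individual to account for correlation among repeated measurements over time".

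Nothing later in the section relaxes this for the two continuous outcomes:

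- Sandwich standard errors are specified only for the GEE model of the cascade outcome.
- The multiply imputed data sets are analysed with the same mixed model.
- The subgroup paragraph carries the models over: "Models will be fit in SAS PROC MIXED and GENMOD, as described above".
- The Power section gives a single SBP SD of 17 with "a within-individual correlation of 0.4 among repeated SBP measurements". For non-HDL it gives "a standard deviation of 41 and a within-individual correlation of 0.7".

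**The concern.** A random intercept with independent, equal-variance residuals is compound symmetry: equal variance at every visit, and the same correlation for visits 4 months apart as for visits 12 months apart. Because the mean model has a common intercept and no arm main effect, β7 is adjusted for baseline through the fitted covariance. The pair that matters most, baseline and month 12, is the pair farthest apart.

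If correlation decays with time at equal SDs, the pooled correlation is too high for that pair and the reported standard error is too small. If the 12-month SD is larger than the pooled SD, the error goes the same way. If the 12-month SD is sufficiently smaller, the standard error is too large and the test is conservative.

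The size of the primary test, and the width of its confidence interval, are at stake. The power simulation as described uses one SD and one correlation per outcome, so it would not reveal the problem.

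**Working it through.** **Inputs from the plan.** N=300, 1:1; two-sided 5%; SBP SD 17 and correlation 0.4; non-HDL SD 41 and correlation 0.7; missing 5%, 10% and 15% at 4, 8 and 12 months. **Assumed here:** the missingness is monotone and unrelated to outcome, and the non-constant covariance patterns are chosen around the plan's values.

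**Step 1: reproduce the plan.** Let V be the true 4×4 covariance and X_i the mean-model design rows for the visits patient i attends. With A = Σ X_i′V_i⁻¹X_i, the standard error of β7 is the square root of the β7 diagonal element of A⁻¹.

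- SBP: SE = 1.941. Power for 6 mmHg = Φ(6/1.941 − 1.960) = Φ(1.131) = 87.1%, against a stated >80%.
- Non-HDL: SE = 3.627. Power for 15 mg/dL = Φ(15/3.627 − 1.960) = 98.5%, against a stated >90%.
- Sample-size table under Power, using N = 300·SE²·(1.960 + z_power)²/δ²: 12 of the 18 entries agree within 3% or 2 patients (for example 350 stated against 355, and 310 against 310). The others are broadly consistent with noise from 1,000 simulations.

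So the plan's figures hold on its own inputs.

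**Step 2: size of the planned test when V is not compound symmetric.** Let W be the compound-symmetry matrix that best fits V, minimising Σ_p π_p{log|W_p| + tr(W_p⁻¹V_p)} over dropout patterns p with probability π_p. Then:

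- reported SE² = β7 element of A⁻¹, where A = Σ X_i′W_i⁻¹X_i
- actual SE² = β7 element of A⁻¹BA⁻¹, where B = Σ X_i′W_i⁻¹V_iW_i⁻¹X_i
- type I error = 2Φ(−1.960 × reported/actual)

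Examples for SBP: with correlations 0.48/0.36/0.24, 1.960 × 1.938/2.082 = 1.824, giving 6.8%. With a 12-month SD of 15, 1.960 × 1.892/1.715 = 2.162, giving 3.1%.

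| Outcome | Correlation at 4/8/12-month lag | SD | Reported SE | Actual SE | Type I error |
|---|---|---|---|---|---|
| SBP | 0.40/0.40/0.40 | 17 | 1.94 | 1.94 | 5.0% |
| SBP | 0.42/0.40/0.38 | 17 | 1.93 | 1.96 | 5.3% |
| SBP | 0.44/0.38/0.32 | 17 | 1.94 | 2.01 | 5.9% |
| SBP | 0.48/0.36/0.24 | 17 | 1.94 | 2.08 | 6.8% |
| SBP | 0.55/0.40/0.25 | 17 | 1.89 | 2.09 | 7.7% |
| SBP | 0.50/0.40/0.30 | rising evenly, 0.90 to 1.06 × 17 | 1.87 | 2.14 | 8.8% |
| SBP | 0.40 constant | 19 at month 12 | 2.00 | 2.17 | 7.2% |
| SBP | 0.40 constant | 15 at month 12 | 1.89 | 1.72 | 3.1% |
| SBP | 0.48/0.36/0.24 | 15 at month 12 | 1.89 | 1.86 | 4.7% |
| Non-HDL | 0.70/0.70/0.70 | 41 | 3.63 | 3.63 | 5.0% |
| Non-HDL | 0.72/0.70/0.68 | 41 | 3.59 | 3.72 | 5.9% |
| Non-HDL | 0.74/0.68/0.62 | 41 | 3.62 | 4.00 | 7.6% |
| Non-HDL | 0.76/0.66/0.56 | 41 | 3.65 | 4.25 | 9.3% |

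**Step 3: simulation check.** 3,000 null trials per scenario, REML random intercept against a REML-type unstructured fit (t with 260 df standing in for Kenward-Roger). The Monte Carlo SE is √(0.05 × 0.95/3000) = 0.4 points.

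| Scenario | Random intercept | Unstructured |
|---|---|---|
| SBP, constant 0.4 | 5.3% | 5.3% |
| SBP, 0.44/0.38/0.32 | 5.5% | 4.9% |
| SBP, 0.48/0.36/0.24 | 7.0% | 5.1% |
| SBP, 0.48/0.36/0.24, 12-month SD 15 | 4.4% | 4.9% |
| SBP, constant 0.4, 12-month SD 15 | 2.9% | 5.0% |
| Non-HDL, constant 0.7 | 5.0% | 5.0% |
| Non-HDL, 0.76/0.66/0.56 | 9.2% | 4.3% |

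**Step 4: power with the unstructured fit, 6 mmHg, N=300.** 83–87% in the equal-SD patterns, 80% with SD rising to 1.06 × 17, and 79% with a 12-month SD of 19. The last figure reflects the larger SD, not the change of model.

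**The case against.** The strongest reply is that no error has been shown. The plan gives one SD and one correlation per outcome and describes its variance components as conservative. On those inputs the planned test is exact. Every departure from 5% comes from a pattern assumed here, and its direction is unknown. That stands, and it limits the finding to a safeguard.

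Other points carry some weight:

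- **Compound symmetry is not strictly necessary.** One of the SBP patterns above is not compound symmetric, yet its size is 4.7% because two departures offset each other. The standard error can be right by coincidence; what is lost is the guarantee.
- **The largest figures are not for the primary outcome.** The 9.2–9.3% values belong to non-HDL. For SBP, mild to moderate decay gives 5.3–5.9%, and the highest simulated SBP rate in Step 3 is 7.0%.
- **Pandemic missingness could soften the effect.** The COVID-19 section lets 4- and 8-month visits go missing while participants stay enrolled, which makes the pooled correlation depend more on the baseline/12-month pair. With an assumed 50% missing at months 4 and 8 and 15% at month 12, independently, 6.8% becomes 6.2%, 7.7% becomes 6.7%, and the non-HDL 9.3% becomes 7.8%. The excess shrinks but remains.
- **Outcome-dependent dropout was not examined.** The statement that only the standard error is affected is limited to the scenarios run.
- **A smaller change exists:** keep the random intercept and add empirical standard errors. That would address the standard error in large samples. It would not improve the weighting, and it does not supply the correct covariance on which likelihood inference under the plan's missing-at-random assumption relies.
- **Aim 2 is the parent trial,** while the document is headed for the Aim 4 substudy. This bears on priority, not on validity.

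**Conclusion.** The point holds. The plan specifies a random intercept and nothing else for the covariance of its primary and main secondary outcomes, so the reported standard error of β7 is assured only under compound symmetry. In the scenarios tabulated above, the true size of the nominal 5% test lies between 3.1% and about 9% for SBP and between 5.0% and 9.3% for non-HDL. The unstructured test stayed at 4.3–5.3% in every scenario simulated in Step 3. These figures rest on N=300, monotone 5/10/15% dropout unrelated to outcome, and assumed covariance patterns. They show a plausible range and do not predict what the trial data will show. β7 is not shown to be biased, the stated power reproduces, and N=300 need not change for this reason. The change should be made because it protects the primary test at very little cost.

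**What to change.** Before unblinded outcome data are analysed, replace the random intercept in the SBP and non-HDL models with `REPEATED month / SUBJECT=id TYPE=UN` and Kenward-Roger degrees of freedom. Keep the common-intercept mean model and the site adjustment.

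State a fallback for non-convergence: heterogeneous Toeplitz (`TYPE=TOEPH`) with `EMPIRICAL` standard errors and a compatible degrees-of-freedom method such as `DDFM=BW`. Use the same specification for the continuous-outcome subgroup models and for the model fitted to each imputed data set.

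The cost is a line or so of SAP text and code, plus the fallback, with no extra patients or visits. The model has 10 covariance parameters instead of 2, estimated from about 300 × (1 + 0.95 + 0.90 + 0.85) = 1,110 observations. The confidence interval may come out slightly wider or narrower, and non-convergence should be rare. If compound symmetry is true, the large-sample SBP standard error stays at 1.94.
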